2.1.1.9 Definition of study phases

Randomized Treatment Phase

The randomized treatment phase starts on the randomization date and ends at the end of treatment date filled on the end of treatment CRF page (For EOT during treatment phase).

Extension Treatment Phase

For the control arm patients going into the cross-over period and receiving Lutathera treatment, the cross-over phase starts at the date of 1st treatment with Lutathera and ends at the end of treatment date filled on the end of treatment cross-over CRF page.

For the investigational arm patients going into the re-treatment period, the re-treatment period starts at the date of 1st re-treatment with Lutathera and ends at the end of treatment date filled on the end of treatment re-treatment page.

Follow-up Phase

The Follow-up phase starts one day after the end of treatment phase/extension phase (whichever was the last phase that the patient completed) and ends at the end of study date filled on the end of study CRF Page.

2.1.1.10 Definition of treatment periods used in analyses

Pre-treatment period:

From day of patient's informed consent to the day before first administration of study treatment in the treatment phase.

Randomized treatment period:

An on-treatment assessment/event during randomized treatment period is defined as any assessment/event in the following time intervals:

- [date of first administration of study treatment, minimum (date of last administration of study treatment in randomized treatment phase + 30 days, 1st injection of Lutathera in extension phase – 1 day)]

Between treatments period:

This period starts from the end of randomized treatment period as defined above to the day before the 1st injection of Lutathera in the extension (cross-over/re-treatment) treatment period. It is not applicable for patients without cross-over/re-treatment and for those who start the cross-over/re-treatment period less than 30 days from the last administration of study treatment in the randomized treatment period.

Cross-over or re-treatment period:

An assessment/event during the cross-over or re-treatment period is defined as any assessment/event in the following time interval:

- [date of first administration (or re-treatment) of Lutathera, date of last administration of study treatment + 30 days]

Note: the calculation of study treatment duration will use different rules as specified in [Section 2.4.1.1](#).

Due to the limited and immature data in cross-over/re-treatment period, efficacy analyses for this period or the corresponding subset will not be generated at the time of primary PFS analysis. Instead, they will be summarized in the future for study update and publication use. Nevertheless, selected key safety output will be generated to include this period for the completeness of safety review.

Note: The date of first administration of study treatment and the date of last administration of study treatment are defined in [Section 2.1.1.4](#) and [Section 2.1.1.5](#), respectively.

Post-treatment follow up period:

The post treatment period is defined as the following:

- For patients who do not receive either cross-over or re-treatment: Post-treatment period starts at the 31st day after the last study treatment administration in the randomized Treatment Phase (i.e., the day after end of on-treatment period) to the End of Study.
- For patients who cross over to Lutathera: Post-treatment period starts at the 31st day after the last study treatment administration in the Extension Treatment Phase (cross-over) to the End of Study.
- For patients who receive re-treatment with Lutathera: Post-treatment period starts at the 31st day after the last study treatment administration in the Extension Treatment Phase (re-treatment) to the End of Study.

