3.4 Optional Re-Treatment Phase

In the Lutathera arm, patients with radiological progression based on RECIST criteria as per central assessment have the option to enroll for post-progression re-treatment, upon signature of a new informed consent, to receive 2 to 4 additional cycles of 7.4 GBq/200 mCi of Lutathera. If RECIST progression occurs after Week 72 post the primary end point analysis, the decision to enroll the patient in re-treatment will be based on local assessment.

Patients who have received Lutathera in Optional Treatment Extension Phase (cross-over) are not eligible for re-treatment with Lutathera.

For enrolment in the optional re-treatment phase, patients must undergo SSTR imaging and meet all requirements listed in Section 5.2.2.

After enrolment into re-treatment phase, patients will initially receive 2 administrations of Lutathera 7.4 GBq/200 mCi at 8-week interval. After that, the Investigator should determine if:

- The patient shows evidence of disease stabilization or response (i.e. absence of radiological progression, or assessed by clinical benefit).
- Has shown good tolerance to Lutathera re-treatment.

If the investigator considers this treatment option in the best interest of the participant and if the participant meets these criteria and agrees to continue with further treatment with Lutathera, the Investigator may administer up to 2 additional administrations of Lutathera 7.4 GBq/200 mCi at 8-week interval. A maximum of 4 administrations of Lutathera is allowed during the re-treatment period.

All safety and efficacy assessments in the re-treatment period will be performed locally and following the schedule in initial treatment period (expression of somatostatin receptors on all target lesions will be evaluated locally before re-treatment; there is no central 'real time' assessment of the SRI images, however the images should be submitted to the central imaging center possibly within 1 month for a second review).

During the re-treatment phase, the administration of SSAs is at investigator's discretion.

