The re-treatment phase will last until locally confirmed disease progression or until EoS, whichever occurs first. If a patient discontinues Lutathera before locally confirmed disease progression in re-treatment, the patient should be followed with tumor assessments as per initial CT/MRI schedule until locally confirmed disease progression. After re-treatment phase is complete, patients will be followed up for 3 years or until EoS, whichever occurs first (and at least 6 months after the last re-treatment dose in the study).

The time window to start re-treatment in this study is within 4 years after the last patient randomized.

For patients in Lutathera arm who are eligible for re-treatment beyond this window, Lutathera access for re-treatment may be granted via Post Study Drug Supply (PSDS) programs, based on local regulation (see Section 9.2.1).

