9.2 Study completion and post-study treatment

Subjects will be followed during the study per the schedule of assessments (refer to Table 8-3 and Table 8-4).

Before the PFS primary analysis (99 evaluable and centrally confirmed disease progressions or death events), patients continue the Treatment Phase until progression; after the PFS primary analysis, the Treatment Phase duration becomes fixed (72 weeks).

Following the end of treatment or early treatment discontinuation, alive patients will enter in the Follow up Phase unless unfeasible (e.g. consent withdrawal, patient lost to follow-up). All treated subjects should have a safety follow up visit conducted 30 days after last administration of study treatment (EoT visit). The information collected is kept as source documentation. Documentation of attempts to contact the subject should be recorded in the source documentation.

At any time during the study (before or after the primary End-Point analysis) any progressive patient (based on central imaging assessment) immediately ceases the Treatment Phase and proceeds to the Follow-up Phase assessment.

Patients randomized in the control arm have the option to enroll for post-progression cross-over upon signature of a new consent (optional Treatment Extension Phase) and receive maximum 4 cycles of Lutathera (7.4 GBq / 200 mCi x 4 cycles; cumulative dose: 29.6 MBq / 800mCi) plus octreotide long-acting every 8 weeks. For these patients, the EoT visit and evaluation of cross-over eligibility can occur on the same day. If these two visits are done on separate days, EoT can be done remotely by phone, and all applicable assessments can be done at the cross-over eligibility visit. If a patient continues to cross-over, 28-day window for EoT visit does not need to apply.

Patients randomized in the Lutathera arm have the option to enroll for post-progression Retreatment Phase upon signature of a new consent and receive 2-4 additional cycles of Lutathera (7.4 GBq / 200 mCi) every 8 weeks. Re-treatment Phase will last until a locally confirmed disease progression or until EoS, whichever occurs first.

The control arm patients who will consent to post-progression cross-over with Lutathera, and the Lutathera arm patients who will consent to post-progression re-treatment with Lutathera, will continue study assessments as planned in Table 8-4; these patients will enter in the Follow up Phase after the end of Lutathera treatment.

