12.6.4 Re-treatment with Lutathera

Safety will be presented in a similar manner to that in Section 12.5.3 for those participants who receive re-treatment with Lutathera during the re-treatment period. The re-treatment period lasts from the date of first administration of re-treatment with Lutathera to progression or death during the re-treatment period.

All information obtained on adverse events will be displayed by subject.

All vital signs data will be listed subject, and visit/time and if ranges are available, abnormalities (and relevant orthostatic changes) will be flagged. Summary statistics will be provided by visit/time.

All ECG data (as per local assessment) will be listed by subject and visit/time, abnormalities will be flagged. Summary statistics will be provided by visit/time.

All laboratory data will be listed by subject, and visit/time and if normal ranges are available abnormalities will be flagged. Summary statistics will be provided by visit/time. Shift tables using the low/normal/high/ (low and high) classification will be used to compare the latest assessment before re-treatment to the worst re-treatment value.

All efficacy analyses for ORR, DoR, PFS, PFS2, and OS will be descriptive. Definitions for ORR, DoR, and PFS (as per local assessment) are the same definitions in Section 12.5.2 except that the baseline will be based on the tumor assessment which demonstrated progression thus allowing re-treatment with Lutathera. Definitions for OS and PFS2 are the same to that in Section 12.5.2 and Section 12.6.1, respectively.

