2.4.1.1 Duration of exposure to study treatment

The duration of exposure to study treatment will be calculated as:

Duration of exposure to study treatment (days) = **(last date of exposure** to any treatment component) – (date of first administration of study treatment component) + 1

The duration of exposure to any single component of study treatment will be calculated as:

Duration of exposure (days) = (last day of exposure to study treatment component) – (date of first administration of study treatment component) + 1

The **last date of exposure** is defined as follows for the study treatment component:

- For Lutathera, the last date of exposure is defined as the last date of administration + 55 days
- For Octreotide LAR, the rules are the following:
 - For patients randomized in the investigational arm, if the last date of administration occurs after an administration of Lutathera, the last date of exposure is defined as the last date of administration for Octreotide + 55 days
 - For patients randomized in the investigational arm, if the last date of administration occurs after the 6-week washout period of the last dose of Lutathera (i.e., Octreotide starts the every 4 weeks schedule after discontinuation of Lutathera), then the last date of exposure is defined as the last date of administration + 27 days
 - For patients randomized in the control arm, the last date of exposure is defined as the last date of administration + 27 days

This duration of exposure includes the periods of temporary interruption (of any component of the study treatment for any reason). The duration of study treatment exposure and exposure to each treatment component will be summarized by treatment group and by treatment period. In addition, number of cycles and average duration of cycle (for Lutathera only) will also be summarized for single component of study treatment by treatment period.

For analyses related to the cross-over/re-treatment period, duration of exposure to Lutathera will be calculated as above during either the cross-over or re-treatment period as appropriate. Since administration of Octreotide LAR is optional in the re-treatment period (expected very few cases), the duration of exposure to Octreotide LAR will not be calculated for the re-treatment period.

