2.8.1 Adverse events (AEs)

All adverse events (AEs), whether or not spontaneously reported by the patient, will be recorded starting from the signing of the ICF until the end of the randomized period/cross-over period/re-treatment period. During the Follow up Phase, only related serious adverse events and adverse events of special interest will be recorded, except for secondary hematological malignancies which will be recorded irrespective of relationship to Lutathera, Octreotide, and amino acid. The data provides information regarding relatedness to Lutathera, Octreotide and amino acid.

AEs that started or worsened during the on-treatment period (including randomized treatment, cross-over and re-treatment periods as defined in [Section 2.1.1.10](#)) is defined as treatment-emergent AEs (TEAE). The primary AE summaries will focus on all treatment-emergent AEs in the randomized treatment period that started or worsened during the randomized treatment

period, defined as from date of first administration of study treatment to 30 days after the date of the last actual administration of any study treatment in the randomized period before cross-over or retreatment. However, selected AE summaries will also be generated for cross-over and re-treatment periods separately. All AEs collected in the eCRF page will be listed along with the information collected e.g., AE relationship to study drug, AE outcome etc. In addition, each AE record in the listings will be flagged for its study period based on the start date.

AEs will be summarized by number and percentage of subjects having at least one AE, having at least one AE in each primary system organ class (SOC) and for each preferred term (PT) using MedDRA coding. A subject with multiple occurrences of an AE will be counted only once in the respective AE category. A subject with multiple CTCAE grades for the same preferred term will be summarized under the maximum CTCAE grade recorded for the event. AE with missing CTCAE grade will be included in the 'All grades' column of the summary tables.

In AE summaries, the primary SOC will be presented alphabetically and the PT will be sorted within primary SOC in descending frequency. For randomized period AE summaries, the sort order for the PT will be based on their frequency in the investigational arm.

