3.1 Power for analysis of key secondary variables

No power calculation has been performed for the key secondary variables.

4 Change to protocol specified analyses

Not applicable

5 Appendix

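### The SAP closes the re-treatment safety period 30 days after the last dose, the protocol runs it to progression or death, and the SAP does not declare the difference

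*SAP*

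**What the plan says.** The documents give several ends to re-treatment.

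- **SAP 2.1.1.10** uses the interval "date of first administration (or re-treatment) of Lutathera, date of last administration of study treatment + 30 days". SAP 2.8.1 takes its treatment-emergent events from this section, and SAP 2.8.3 restricts laboratory summaries to the same 30 days.
- **Protocol 12.6.4**, the section on analysing re-treatment: "The re-treatment period lasts from the date of first administration of re-treatment with Lutathera to progression or death during the re-treatment period".
- **Protocol 3.4**, on conduct: "The re-treatment phase will last until locally confirmed disease progression or until EoS, whichever occurs first". Table 8-3 agrees. Its re-treatment column continues assessments to progression and places the end-of-treatment visit after that.
- **SAP 2.1.1.9** ends re-treatment at the end-of-treatment date on the re-treatment CRF page, which under Table 8-3 is reached at progression.
- **Protocol 9.2** repeats the progression-or-EoS rule, but then says of cross-over and re-treated patients together that "these patients will enter in the Follow up Phase after the end of Lutathera treatment".

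On collection, SAP 2.8.1 has all adverse events recorded "until the end of the randomized period/cross-over period/re-treatment period". In follow-up, recording narrows to related serious events, related events of special interest, and secondary hematological malignancies whatever their cause. SAP Section 4, headed "Change to protocol specified analyses", states that there is nothing to report.

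**The concern.** Safety during re-treatment is a named exploratory objective in both documents. A programmer working from the SAP and one working from protocol 12.6.4 would produce different re-treatment tables from the same data, and nothing in the SAP tells the reader that a choice was made. The part removed is the time between 30 days after the last dose and progression, which is where any late toxicity of a second course would appear. If the follow-up sentence in 9.2 were applied literally, the loss would come earlier: many of those events would not be collected at all.

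**Working it through.** The documents give no figure for the size of this difference, so there is none to reproduce. What can be computed is how much of the protocol's period falls outside the SAP's.

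**Inputs**
- Dosing (protocol 3.4): "patients will initially receive 2 administrations of Lutathera 7.4 GBq/200 mCi at 8-week interval", with up to 2 further doses at the same interval. Doses are therefore 56 days apart, 2 to 4 in number.
- SAP tail: 30 days after the last administration, both end days counted.
- Octreotide would extend the window, because SAP 2.1.1.5 counts any treatment component. SAP 2.4.1.1 expects very few such cases in re-treatment, so it is ignored here.
- Time to progression: 12.52 months, the median PFS that protocol 4.1 quotes from a meta-analysis. This is an assumption for the present trial. In days, 12.52 × 30.4375 = 381.

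**Formulas**
- SAP window W = 56 × (doses − 1) + 30 + 1 days.
- Share outside for a patient progressing at the median = (381 − W) / 381.
- Share of person-time outside if progression times are exponential with that median = exp(−W × ln 2 / 381).

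| Doses | W (days) | Days after window | Outside, median patient | Outside, exponential |
|---|---|---|---|---|
| 2 | 56 + 31 = 87 | 294 | 77% | 85% |
| 3 | 112 + 31 = 143 | 238 | 62% | 77% |
| 4 | 168 + 31 = 199 | 182 | 48% | 70% |

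The window closes at week (56 + 30)/7 = 12.3 after 2 doses and (168 + 30)/7 = 28.3 after 4. Footnote 10 to Table 8-3 names re-treatment visits from week 32 to week 68, and the table records adverse events at each. All of these fall after the window has closed. So do the 12-weekly laboratory tests that protocol 8.5.2 schedules once Lutathera has ended.

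**Sensitivity to the median.** With an assumed median of 6 months (6 × 30.4375 = 183 days), the shares outside are (183 − 87)/183 = 52%, (183 − 143)/183 = 22%, and none for 4 doses, whose window of 199 days is longer than the median.

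**From time to events.** Let r be the onset rate after the window divided by the rate inside it. The share of events outside is r × (381 − W) / [W + r × (381 − W)]. The documents give no value for r, so a range is shown for the median patient with 2/3/4 doses:
- r = 1: 77/62/48%
- r = 0.5: 63/45/31%
- r = 0.25: 46/29/19%
- r = 0.1: 25/14/8%

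More than half the events fall outside only if r exceeds W/(381 − W), which is 0.30, 0.60 and 1.09.

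The calculations take dosing as on schedule and ignore truncation at EoS.

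**The case against.** The best defence is that protocol 12.6.4 opens by asking for re-treatment safety to be presented in the manner of 12.5.3, which itself uses last dose + 30 days. On that reading the SAP follows the protocol. But that sentence concerns presentation, and the next one defines the re-treatment period expressly. A general cross-reference does not override a specific definition. At the least, the wording is ambiguous and the SAP should say which reading it takes.

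It is also fair that later events do not disappear. All collected adverse events are listed and flagged by period. Events of special interest are summarized over the whole study. Time to first secondary hematological malignancy or nephrotoxicity uses all periods. Deaths are summarized for post-treatment follow-up, and all laboratory data are listed. This stands and limits the harm. It does not restore a re-treatment-specific summary: the whole-study summaries of special-interest events are by treatment arm and so combine initial treatment with re-treatment.

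The objection that 12.52 months comes from outside the trial also stands, and the percentages are conditional on it.

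A reader might infer that the randomized-period window is faulty too, because SAP 2.4.1.1 says "For Lutathera, the last date of exposure is defined as the last date of administration + 55 days" while events are counted for only 30 days. The documents do not support that. The 30-day rule there matches protocol 12.5.3, SAP 2.1.1.10 states that exposure duration follows different rules, and octreotide continued after Lutathera stops keeps the window open. A 55-day window for one arm would be a debatable trade-off, not a correction.

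**Conclusion.** The two definitions conflict and the SAP does not declare it. Events and laboratory values arising more than 30 days after the last re-treatment dose and before progression drop out of the re-treatment adverse event and laboratory summaries. At the assumed 12.52-month median, and with dosing on schedule, 77/62/48% of the protocol's period lies outside the SAP window for 2/3/4 doses.

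It is tempting to go on and say that most adverse events are lost. The documents do not support this. They give no onset times relative to dosing, and the claim fails if events cluster around doses.

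The re-treatment analysis is exploratory and descriptive, and the primary and key secondary tests are untouched. The point is minor.

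**What to change.** - **SAP 2.1.1.10:** give the re-treatment period the end defined in protocol 12.6.4, which is consistent with the re-treatment end-of-treatment date in SAP 2.1.1.9. Carry it through to the laboratory rule in SAP 2.8.3. Show last dose + 30 days as a secondary summary.
- **If the sponsor prefers the 30-day cut:** keep it, but list and justify it in SAP Section 4.
- **Protocol 9.2:** reconcile the sentence on entering follow-up with 3.4, the rest of 9.2 and Table 8-3, so that it is clear what is collected between the last re-treatment dose and progression.

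The cost is one date derivation, some SAP wording and one protocol sentence. The drawback is that recording may be incomplete beyond 30 days for patients who leave the re-treatment phase early, so the longer summary should state how many patients are affected. The randomized-period window needs no change on this account.
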